7.3 Study Drug or Device Procedures

At visits 1 and 3, the following procedures will be done for study specific purposes in addition to standard of care procedures:

- Schirmer's Test with anesthesia (may be standard of care)
- Ocular Surface Disease Index questionnaire
- Symptom Assessment iN Dry Eye questionnaire
- Central Cornea In Vivo Confocal Microscopy (may be standard of care)
- Corneal fluorescein staining

At visit 2, the following procedures will be done for study specific purposes:

- Eye examination (best corrected visual acuity, bio-microscopy, applanation tonometry, funduscopy)
- Tear Break-up Time
- Corneal fluorescein staining
- Conjunctival lissamine green staining
- Schirmer's Test with anesthesia
- Ocular Surface Disease Index questionnaire

- Symptom Assessment in Dry Eye (SANDE) questionnaire
- Central Cornea In Vivo Confocal Microscopy

7.4 Standard of Care Procedures

The following procedures are the standard of care:

- Eye examination (best corrected visual acuity, bio-microscopy, applanation tonometry, funduscopy)
- Tear Break-up Time
- Corneal fluorescein staining
- Conjunctival lissamine green staining
- Schirmer's Test with anesthesia (may be study specific)
- Central Cornea In Vivo Confocal Microscopy (may be study specific)

7.5 Follow-up Procedures

After enrollment, the subjects will be scheduled for a second visit (Week 2 ± 3 days) and a third visit (Week 6 ± 1 week).

The following procedures will be performed at all follow-up visits:

- Eye examination (best corrected visual acuity, bio-microscopy, applanation tonometry, funduscopy)
- Tear Break-up Time
- Corneal fluorescein staining
- Conjunctival lissamine green staining
- Schirmer's Test with anesthesia
- Ocular Surface Disease Index questionnaire
- Symptom Assessment in Dry Eye (SANDE) questionnaire

• Central Cornea In Vivo Confocal Microscopy

7.6 Unscheduled Visits

If the subject reports to the Cornea Department for a visit that is not related to the study, only a review of adverse assessments will be required per the study.

7.7 Early Termination

If a subject withdraws or is withdrawn from the study prior to completion of all study visits, there will be no additional procedures performed

7.8 Schedule of Activities (Study Table)

Т	able1- Schedule	e of events ar	ıd procedu	res	
Visit#	1			2	3
Visit Description	Screening	Baseline	Day 1	Week 2	Week 6 (±
				(± 3 days)	1 week)
Obtain Informed Consent	X				
Inclusion/ exclusion criteria	X				
Medical and Ophthalmic History	X		START OF STUDY MEDICATION	X	X
Medication History	X		DICA		
BCVA	X		Y ME	X	X
OSDI		X	IUD	X	X
SANDE		X	OF S	X	X
TBUT	X		ART	X	X
Biomicroscopy	X		ST	X	X
Corneal staining	X			X	X
Schirmer with anesthesia	X			X	X
Conjunctival staining	X			X	X

Intraocular Pressure	X		X	X
Funduscopy	X		X	X
In vivo confocal	X		X	X
microscopy				
Concommitant			X	X
medications				
Compliance and	X	X	X	X
adverse events check				

8. SAFETY AND EFFECTIVENESS ASSESSMENTS

8.1 Safety Assessments

The primary safety variable monitored will be the occurrence of adverse events. The severity of each adverse event observed will be evaluated as serious or not serious and the occurrence will be evaluated as expected or unexpected. The relationship of the event to the study medication will be assessed by the investigator as possibly, probably, or definitely related. Safety variables will be evaluated at all study visits. If adverse events occur, the first concern will be the safety of the study participants. Any serious adverse event occurring during the study period will be immediately reported to MEEI IRB. At each visit throughout the study, the investigator will begin querying for adverse events by asking each subject a general, non-directed question such as "How have you been feeling since the last visit?" or "How have your eyes been since the last visit?"

The investigator will ask questions to subjects at each visit to determine if they have had any changes to the use of concomitant medications since the previous visit. A comprehensive eye examination including best-corrected visual acuity, measuring intraocular pressure, evaluation of the condition of conjunctiva, cornea, anterior chamber, iris/pupil, lens, vitreous, macula and optic nerve will be performed. Any changes in the study eyes from the screening visit will be recorded. If a subject contracts infectious conjunctivitis, they will be instructed to discard the remainder of the study drug and new drug will be sent from the host site pharmacy, Massachusetts Eye and Ear Infirmary.

If treatment with artificial tears is inadequate, or the subject develops severe form of ocular surface disease and dry eye, for the safety and proper treatment of the subject, the investigator can unmask the subject's treatment assignment to determine which

treatment has been assigned and institute appropriate follow-up care. However, the subject will be kept in the study so we can do the "intent-to-treat" analysis.

Withdrawal from the study will happen if any of the following occurs:

- Investigator determination that it is not in the best interest of the subject to continue participation.
- Subject's wish to withdraw for any reason.

After being withdrawn, subjects will be followed according to each case until the adverse event is resolved.

8.2 Effectiveness Assessments

Comparison of the efficacy of the taper Lotemax versus artificial tear will be evaluated using both clinical and IVCM parameters which include the followings:

Ocular Signs

- Corneal epitheliopathy (corneal fluorescein staining using the NEI grading scheme). (Appendix IV)
- Conjunctival epitheliopathy (conjunctival lissamine green staining using NEI grading scheme). (Appendix IV)
- > Tear Film Break Up Time (TBUT)
- Schirmer's Test with Anesthesia

Ocular Symptoms

- Ocular Surface Disease Index (OSDI) questionnaire. (Appendix II)
- > Symptom Assessment iN Dry Eye (SANDE) questionnaire. (Appendix III)

In Vivo Confocal Microscopy

- > Superficial corneal epithelial cells: Density, size, and hypereflectivity
- > Corneal subbasal immune dendritiform cells: Density, size, and cell field
- > Corneal subbasal nerves: Number and length of the total, main nerves and the branches

9. ADVERSE EVENT RECORDING AND REPORTING

9.1 Recording Requirements

Research subjects will be routinely questioned about adverse events at study visits. All observed or volunteered adverse events (serious or non-serious) and abnormal test findings, regardless of study group or suspected causal relationship to the study drug(s) or device(s) will be recorded in the subjects' case histories (source data, case report form). For all adverse events, sufficient information will be pursued and/or obtained so as to permit 1) an adequate determination of the outcome of the event (i.e., whether the event should be classified as a serious adverse event) and; 2) an assessment of the causal relationship between the adverse event and the study drug(s) or device(s).

Adverse events or abnormal test findings thought to be associated with the study drug(s) or device(s) will be followed until the event (or its sequel) or the abnormal test finding resolves or stabilizes at a level acceptable to the Investigator.

An abnormal test finding will be classified as an adverse event if one or more of the following criteria are met:

- The test finding is accompanied by clinical symptoms
- The test finding necessitates additional diagnostic evaluation(s) or medical/surgical intervention; including significant additional concomitant drug treatment or other therapy
- The test finding leads to a change in study drug dosing or discontinuation of subject participation in the clinical research study
- The test finding is considered an adverse event by the Investigator. Note: simply repeating a test finding, in the absence of any of the other listed criteria, does not constitute an adverse event.

The Investigator will promptly review documented adverse events and abnormal test findings to determine 1) if the abnormal test finding should be classified as an adverse event; 2) if there is a reasonable possibility that the adverse event was caused by the study drug(s); and 3) if the adverse event meets the criteria for a serious adverse event.

If the Investigator's final determination of causality is "unknown and of questionable relationship to the study drug(s)", the adverse event will be classified as associated with the use of the study drug(s) for reporting purposes. If the Investigator's final determination of causality is "unknown but not related to the study drug(s)", this determination and the rationale for the determination will be documented in the respective subject's case history (source data or case report form).

9.2 REPORTING PROCEDURES

> REPORTING OF ADVERSE EVENTS TO FDA

If an investigator determines that a serious adverse event (SAE) is related to one of the study medications the SAE will be reported to the FDA.

Reporting Adverse Events to Other External Entities

The sponsor (GSK) does not require reports on adverse events. Therefore no reports on adverse events will be submitted to external entities.

Reporting Adverse Events to the Human Studies Committee

MEEI HSC policy for "Reporting Adverse Events and Unanticipated Problems" will be followed.

9.3 Withdrawal of Subjects due to Adverse Events

Withdrawal from the study will happen if any of the following occurs:

- Investigator determines that is not in the best interest of the subject to continue participation.
- Subject's wish to withdraw for any reason.

ter being withdrawn, subjects will be followed according to each case untiverse event is resolved.	il the

10. STATISTICAL METHODS/DATA ANALYSIS

10.1 Primary endpoint(s) or outcome measure(s)

In Vivo Confocal Microscopy

- > Superficial corneal epithelial cells: Density, size, and hypereflectivity
- > Corneal subbasal immune dendritiform cells: Density, size, and cell field
- > Corneal subbasal nerves: Number and length of the main nerves and the branches

10.2 Secondary endpoints or outcome measure(s)

Ocular Signs

- > Corneal epitheliopathy (corneal fluorescein staining using the NEI grading scheme). (Appendix IV)
- Conjunctival epitheliopathy (conjunctival lissamine green staining using NEI grading scheme). (Appendix IV)
- > Tear Break Up Time (TBUT)
- > Schirmer's Test with Anesthesia
- ➤ Intraocular pressure (IOP) by measure of applanation tonometry

Ocular Symptoms

- > Ocular Surface Disease Index (OSDI) questionnaire. (Appendix II)
- > Symptom Assessment iN Dry Eye (SANDE) questionnaire. (Appendix III)

10.3 Sample Size Determination

To calculate sample size, density of sub-basal dendritic cells in the central cornea was used as an outcome measure. Based on a previous published paper (Villani et al, Innate Immunity. 2013;19(4) 420–427), a difference of 52 cell/mm² with a standard deviation of 44 were used to calculate the sample size with the following formula:¹⁻³ $4 \times \sigma^2 \times Z(1 - \alpha/2)^2$

$$N = \frac{4 \times \sigma^2 \times Z(1 - \alpha/2)^2}{d^2}$$

With $\alpha = 0.05$ ($Z_{\alpha} = 1.96$), d = 52, and p = 44, a sample size of 22 was calculated for each group (44 for both groups). To compensate for potential loss to follow-up, a total of 50 subjects will be enrolled in this study.

- 1) Daniel WW. Biostatistics: a foundation for analysis in the health sciences 7th ed. New York, NY: Wiley, 1999; 180-185, 268–270.
- 3) Eng G. Sample size estimation: how many individuals should be studied? Radiology. 2003; 227:309-13.

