3. STUDY DESIGN

3.1 Study Design Description

This is a single site, prospective, randomized, controlled, double-masked clinical trial including 50 subjects with DED. The participants will be randomized to take either Lotemax or Soothe Tired Eyes Lubricant Eye Drops for 6 weeks. Both Lotemax and the artificial tear will be used 4 times a day for 2 weeks, 2 times a day for 2 weeks, and once a day for 2 weeks. After screening/baseline examination and enrolling into the study, the participants will have follow-up visits at 2 weeks as well as 6 weeks.

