10.5 Effectiveness Analysis

For efficacy variables and any other variables except for safety, all subjects will be analyzed with the treatment to which they were randomized (the intent-to-treat population). Subjects that are not compliant with the study medication or study procedures may or may not be withdrawn according to the investigators discretion. Subjects that are noncompliant, but remain active in the study, will be followed so that an intent-to-treat analysis can be conducted. For safety variables, subjects will be analyzed with the treatment actually received (the safety population).

The primary analysis for the proposed study will be based on a standard intention-to-treat analysis with each study participant analyzed with respect to the randomized treatment assignment, regardless of eventual compliance. A secondary analysis may include imputation of missing data for select variables. A per-protocol analysis, disqualifying subjects or subject visits, might also be done, but is not planned because observational analyses of actual treatment use could introduce bias if the pattern of use is in some way related to the outcome.

Despite the randomized nature of the treatment assignments, in this relatively small sample of study subjects there may be imbalances with regard to potential confounding variables. Thus, as an initial step in the analysis, we will compare those assigned to Lotemax versus those randomized to the artificial tear with regard to demographic characteristics and potential confounding variables, using the non-parametric Wilcoxon rank sum test for continuous or ordinal variables, and chisquare or Fisher's exact tests for categorical variables.

The changes in primary end-points within each group during the course of treatment will be analyzed using Analysis of Variance (ANOVA) with post hoc analysis of Bonferroni correction. The values between the Lotemax and artificial tear groups will be compared with non-parametric Wilcoxon rank sum test. P values of 0.05 or less will be considered as statistically significant.

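### Section 10.3: the printed sample-size formula gives 11.0, not the stated 22 per group, and no power is stated; this is a derivation and reporting error, not evidence that the trial is too small

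*Combined protocol and SAP*

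**What the plan says.** Section 10.3 (Sample Size Determination) takes its inputs from one published paper: "a difference of 52 cell/mm² with a standard deviation of 44 were used to calculate the sample size". It then prints a formula, N = 4 × σ² × Z(1−α/2)² / d², and inserts α = 0.05 (Z = 1.96), d = 52 and 44. The symbol beside the 44 is printed as p, but the preceding sentence makes clear that it is the standard deviation. The result is given as "a sample size of 22 was calculated for each group (44 for both groups", and the total is raised to 50 for loss to follow-up. The section does not say whether N in the formula is per group or in total.

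Section 10.5 (Effectiveness Analysis) names the between-group test: "The values between the Lotemax and artificial tear groups will be compared with non-parametric Wilcoxon rank sum test", with significance at 0.05. Section 10.1 lists several confocal-microscopy measures as primary, of which the sizing variable is one part of one line: "Corneal subbasal immune dendritiform cells: Density, size, and cell field". Section 3.1 says that "the participants will have follow-up visits at 2 weeks as well as 6 weeks". Section 10.3 does not say which of these visits the difference of 52 refers to.

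**The concern.** A reader who puts the printed inputs into the printed formula does not get the printed answer, and the gap is a factor of two, too large to be rounding. The formula also contains only Z(1−α/2). It has no term for power, and no target or achieved power appears in Section 10.3 or elsewhere, although the planned between-group analysis is a hypothesis test.

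This paragraph is the only justification for enrolling 50 people. The two candidate sizes are not interchangeable: one gives moderate power for the planned test and the other gives high power. As written, the reader cannot tell which criterion the sponsor meant to meet.

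**Working it through.** **Inputs.** d = 52 cells/mm², σ = 44, two-sided α = 0.05 (Z = 1.96), all from Section 10.3; 1:1 allocation from Section 3.2.1; Wilcoxon rank sum test from Section 10.5.

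**Step 1: the plan's own figure.** Printed formula with printed inputs:

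4 × 44² × 1.96² / 52² = 4 × 1936 × 3.8416 / 2704 = 11.002

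The stated figure is 22 per group. If N is per group, the formula gives half of it. If N is a total, the formula gives 11.002 / 2 = 5.5 per group, a quarter of it. No reading of N gives 22 per group.

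**Step 2: what would give about 22.** Several routes do, and none of them is printed:

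- A factor of 8 in place of 4: 8 × 1936 × 3.8416 / 2704 = 22.004 per group. At that size a 95% confidence interval for the difference has total width 2 × 1.96 × 44 × √(2/22) = 52.0. At 11 per group the width is 73.5.
- A two-sample formula with 97.5% power. This is algebraically the same, because 2 × (1.96 + 1.96)² = 8 × 1.96².
- A two-sample formula at 80% power: 11.24 per group, total 22.48, with the total then reported as if it were per group.
- The printed formula read as a precision formula for one mean: at n = 11 the 95% interval has total width 2 × 1.96 × 44 / √11 = 52.0. Two groups then make 22, and that total would have been doubled again.

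The first two would make 22 per group the intended number. The last two would make it a total mislabelled as per group. The documents do not settle which applies.

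**Step 3: power at each size.** For the t-test, the noncentrality is (d/σ) × √(n/2): 3.92 at n = 22 and 2.77 at n = 11. The normal approximation is Φ(noncentrality − 1.96). Wilcoxon power is from 400,000 simulations of normal data with the exact critical value.

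| n per group | Wilcoxon | t-test | Normal approximation |
|---|---|---|---|
| 11 | 71.9% | 75.1% | 79.2% |
| 22 | 96.1% | 96.9% | 97.5% |

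**Step 4: smallest difference detectable at 22 per group, SD 44.** By normal approximation, 80% power needs 44 × √(2/22) × (1.96 + 0.84) ≈ 37.2 and 90% needs about 43.0. By t-test the values are 38.0 and 44.0. By Wilcoxon, power is 77.6% at 38, 79.7% at 39, 89.7% at 45 and 90.9% at 46, so about 39 and 45.

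**Step 5: sensitivity to the SD (d = 52, 22 per group).** The SDs of 50 and 60 are assumptions.

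| SD | Wilcoxon | t-test |
|---|---|---|
| 44 | 96.1% | 96.9% |
| 50 | 90.6% | 92.1% |
| 60 | 77.9% | 80.2% |

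**The case against.** The best case for the plan is that this is a documentation slip that runs in the safe direction. Nobody proposes 11 per group; Sections 3.1 and 10.3 both say 50 subjects, and on the printed inputs a standard two-sample calculation needs only 12 per group for 80% power and 16 for 90%. A formula without a power term can also be legitimate if the aim is a confidence interval of a given width. That part stands: the missing term is not an error in itself, and the arithmetic gives no reason to enrol more people. But no precision aim is stated either, and the printed formula does not deliver 22 under a precision reading any more than under a power reading.

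The opposite caution also stands. High power at 22 per group cannot be taken as established, because Section 10.3 does not say whether 52 is a difference between treatments, a change over time or some other contrast in the cited paper. Sections 4.1 and 4.2 also select on dendritic cell count, so the SD and the shape of the distribution in this trial may differ from the source. The power figures are therefore conditional. Neither point makes 11.0 equal to 22.

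**Conclusion.** The concern holds. The stated 22 per group does not follow from the formula and inputs in Section 10.3, which give 11.0, and the documents state neither the criterion that 22 was meant to satisfy nor its power. The error is in derivation and reporting and should be fixed. It does not show that the trial is under-powered.

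The conclusion about power rests on d = 52 and SD = 44 applying to the between-group comparison, on normal data, on two-sided α = 0.05, and on 22 evaluable subjects in each group. It concerns dendritic cell density alone and makes no allowance for the other primary measures in Section 10.1. The mismatch between 11.0 and 22 needs none of these assumptions; it follows from the printed text alone.

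**What to change.** Keep 44 evaluable and 50 enrolled. In Section 10.3, either print the formula that was actually used, saying that N is per group, or remove the statement that 22 follows from the printed one. Confirm that the 44 is σ. Then state what 22 per group delivers for the planned test, for example:

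> With 22 evaluable subjects per group, a true difference of 52 cells/mm² in central corneal sub-basal dendritic cell density at [visit to be specified], an SD of 44 and two-sided α of 0.05, the Wilcoxon rank sum test has about 96% power (simulation, normal data; 96.9% by t-test). It has 80% power for a difference of about 39 cells/mm². These figures depend on SD = 44, apply to this single measure and make no allowance for the other listed primary measures.

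The sponsor must name the visit, since there are two follow-up visits and Section 10.3 names neither. It should also say which contrast in the cited paper the 52 and 44 come from. The cost is one rewritten paragraph, with no change to enrolment, visits or analysis.

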10.4 Analysis Population

N/A

10.5 Effectiveness Analysis

For efficacy variables and any other variables except for safety, all subjects will be analyzed with the treatment to which they were randomized (the intent-to-treat population). Subjects that are not compliant with the study medication or study procedures may or may not be withdrawn according to the investigators discretion. Subjects that are noncompliant, but remain active in the study, will be followed so that an intent-to-treat analysis can be conducted. For safety variables, subjects will be analyzed with the treatment actually received (the safety population).

The primary analysis for the proposed study will be based on a standard intention-to-treat analysis with each study participant analyzed with respect to the randomized treatment assignment, regardless of eventual compliance. A secondary analysis may include imputation of missing data for select variables. A per-protocol analysis, disqualifying subjects or subject visits, might also be done, but is not planned because observational analyses of actual treatment use could introduce bias if the pattern of use is in some way related to the outcome.

Despite the randomized nature of the treatment assignments, in this relatively small sample of study subjects there may be imbalances with regard to potential confounding variables. Thus, as an initial step in the analysis, we will compare those assigned to Lotemax versus those randomized to the artificial tear with regard to demographic characteristics and potential confounding variables, using the non-parametric Wilcoxon rank sum test for continuous or ordinal variables, and chisquare or Fisher's exact tests for categorical variables.

The changes in primary end-points within each group during the course of treatment will be analyzed using Analysis of Variance (ANOVA) with post hoc analysis of Bonferroni correction. The values between the Lotemax and artificial tear groups will be compared with non-parametric Wilcoxon rank sum test. P values of 0.05 or less will be considered as statistically significant.

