3.2.1 Randomization Procedures

Once the investigator determines that the subject has met all of the inclusion and exclusion criteria, the subject will be randomized to take either Lotemax or Soothe Tired Eyes Lubricant Eye Drops (artificial tears). The randomization will be in a 1:1 ratio using a permuted-block design (which will be obtained using a computer-based random code generator) into the two groups.

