5.5 Other Medications

Administration

The use of any concurrent, prescription, or over-the-counter medication, is to be recorded along with the reason the medication was taken. During the study, all concomitant medication treatment regimens, ocular hygiene treatments (i.e., lid scrubs and warm compresses), or insertion of punctal plugs will be kept as constant as permitted by accepted medical practice.

Using artificial tears (preserved and non-preserved) are permissible at the screening visits and during the study. However, concomitant use of artificial tears will be monitored. At each study visit, subjects will be queried about the average number of times they used artificial tears each day during the past week and the number of days during the past week when they did not use any artificial tears.

Systemic and topical ophthalmic medications, that the subjects are already taking as part of their current treatment for dry eye disease will be maintained, without a change in frequency.

When necessary, treatment and administration of any other therapy, besides their current and study's regimen, will be done as the safety of the study participant is the primary consideration. The administration of a prohibited medication or procedure will be considered a protocol violation and the subject may be discontinued from the study. Prohibited medications include other ophthalmic steroids. Prohibited procedures include any ocular surgery.

• Rescue Medication or Therapy

When necessary, administration of any other therapy besides the study medication and their current medications will occur for the safety of the subject, which is the primary concern. If treatment with artificial tears is inadequate, or if the subject develops a severe form of ocular surface disease and dry eye, the subject may be unmasked by the investigator. To ensure the subject's safety and proper treatment, unmasking of the study treatment assignment will allow the investigator to institute appropriate follow-up care. The subject will be kept in the study so that we can do an "intention to treat" analysis.

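### Section 10.5 answers expected chance imbalance only with baseline significance tests and then an unadjusted comparison; the tests neither detect nor correct an imbalance that matters, and their consequence is unstated.

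*Combined protocol and SAP*

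**What the plan says.** Section 10.5 notes that the sample is small and that the arms may differ on potential confounders. Its response is that "as an initial step in the analysis, we will compare those assigned to Lotemax versus those randomized to the artificial tear" on demographic and potential confounding variables, "using the non-parametric Wilcoxon rank sum test for continuous or ordinal variables" and chi-square or Fisher's exact tests for categorical ones. The section's only significance threshold is 0.05.

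The section does not list the confounders, attach a consequence to either test result, or name an adjusted model. The between-arm efficacy comparison is a Wilcoxon rank sum test without covariates.

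Nor does the design control imbalance beforehand. Section 3.2.1 states: "The randomization will be in a 1:1 ratio using a permuted-block design". It names no stratification factor. Background treatment can differ between subjects: section 4.2 excludes a recent change in the frequency of topical cyclosporine or oral tetracyclines, not their use, and section 5.5 adds: "Systemic and topical ophthalmic medications, that the subjects are already taking as part of their current treatment for dry eye disease will be maintained".

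**The concern.** If allocation was done properly, any baseline difference is due to chance, so a baseline P value tests a hypothesis already known to be true. Failure to reach significance in a small trial is not evidence of balance. Whether an imbalance matters depends on its size and on how strongly the variable predicts outcome. The P value does not measure the second of these at all.

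The plan therefore raises a problem and gives it a response that cannot settle it. Three things are at stake:

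- precision, because outcome variation that baseline variables explain stays in the error term;
- conditional bias, in the particular trial where a prognostic variable happens to be unbalanced;
- discretion, because nothing says whether a flagged variable would lead to an adjusted analysis, a caveat or nothing.

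**Working it through.** **Inputs.** Section 10.3: "a total of 50 subjects will be enrolled in this study", which is 25 per arm at 1:1. The same section gives "d = 52, and p = 44, a sample size of 22 was calculated for each group", with 44 the standard deviation, in cells/mm². The step from 44 to 50 subjects is made "To compensate for potential loss to follow-up": 44/(1 − 0.12) = 50, an implied loss of 12%. The formula printed in 10.3 gives 4 × 44² × 1.96²/52² = 11.0, half of the stated 22. That is a separate matter. Here 25 and 22 are used only as arm sizes and 44 only as a scale.

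**1. What the baseline test can see.** The smallest mean difference that reaches two-sided P = 0.05, in SD units, is 1.96 × √(2/n).

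- n = 25: 1.96 × √(2/25) = 0.554 SD. On the SD of 44 this is 24 cells/mm², or 47% of the planned difference of 52.
- n = 22: 1.96 × √(2/22) = 0.591 SD.

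In 20,000 simulated null trials at 25 per arm with normal data, the Wilcoxon test flagged 4.9% of variables, all by chance. It left 84% of observed differences between 0.50 and 0.55 SD unflagged.

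A categorical illustration, with assumed counts: 12/25 against 6/25 users of a background drug (48% against 24%) gives Fisher P = 0.14 and uncorrected chi-square P = 0.08. Neither is flagged.

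**2. How often a sizeable imbalance goes unflagged.** The standard error of the difference is √(2/25) = 0.283 SD, so 0.30 SD corresponds to z = 0.30/0.283 = 1.06. P(1.06 < |Z| < 1.96) = 0.239, or about 24% of trials for any one continuous variable.

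**3. Effect on the treatment comparison.** Let ρ be the covariate-outcome correlation; the documents give no value. With baseline difference z, the null test statistic is N(ρz, 1 − ρ²), and conditional type I error is P(|N(ρz, 1 − ρ²)| > 1.96).

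| Unadjusted comparison, type I error | ρ = 0.5 | ρ = 0.7 |
|---|---|---|
| Averaged over imbalances of 0.30–0.55 SD | 7.7% | 9.3% |
| Averaged over all unflagged trials | 4.3% | 3.5% |
| At z = 1.9 (0.54 SD), just below the flag | 12.2% | 18.9% |
| Over all randomisations | about 5% | about 5% |

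**4. Precision.** For an assumed effect of 0.7 SD at 25 per arm, adjustment for one prespecified covariate divides the effect in residual SD units by √(1 − ρ²). Power comes from the noncentral t distribution with 47 degrees of freedom and noncentrality 0.7/√(1 − ρ²)/√(2/25)/√(1 + 1/47). The last term allows for chance imbalance.

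| | Power |
|---|---|
| Unadjusted t test (48 df) | 68% |
| Adjusted, ρ = 0.2 | 69% |
| Adjusted, ρ = 0.3 | 71% |
| Adjusted, ρ = 0.5 | 79% |
| Adjusted, ρ = 0.7 | 92% |

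The planned rank sum test had about 64 to 66% in simulation with normal data. Adjusting only after a significant baseline test gave 68% (ρ = 0.5) and 70% (ρ = 0.7), with type I error of 4.6% and 3.5%. That recovers almost none of the gain.

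**The case against.** The strongest reply is that the baseline tests do nothing. As written, the between-arm analysis is one unadjusted rank sum test whatever they show, so they cannot alter the treatment result. This largely stands. A reader might infer from the reference to confounding that the tests decide what is adjusted for, or that a non-significant variable will be declared balanced. Section 10.5 says neither. What remains is that an acknowledged imbalance goes untreated if the tests drive nothing, and that the rule is unstated if they drive something.

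A reader might also infer an inflated false-positive rate, citing the 12% and 19% figures. Those belong to the extreme edge of the unflagged range: an imbalance of 0.50 to 0.55 SD occurs in only about 2.7% of trials per variable. Over all randomisations the error rate stays near 5%, and test-then-adjust does not raise it.

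Nor do the documents support correlations of 0.5 to 0.7 for yes/no medication use. For a binary covariate with prevalence p, the implied user/non-user difference is ρ × 44/√(p(1 − p)). At ρ = 0.5 that is 22/0.5 = 44 cells/mm² for p = 0.5 and 22/0.4 = 55 for p = 0.2. At ρ = 0.7 it is 62 and 77. These are close to or above the planned treatment difference of 52. Such correlations are more natural for the outcome's own baseline value.

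Finally, the chance of at least one false flag, 1 − 0.95¹⁰ = 40% for ten variables, assumes both the number and their independence. The plan lists none, and dry eye measures are plausibly correlated.

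**Conclusion.** The point holds as a weakness of method and an omission, not as an error that invalidates the primary test. Baseline significance testing is the plan's only response to an imbalance it anticipates. At 25 per arm it can pass differences of up to about 0.55 SD (0.59 SD at 22), and no consequence is specified.

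The size depends on ρ, which is assumed throughout. At 0.5 to 0.7, conditional type I error averages about 8 to 9% over imbalances of 0.30 to 0.55 SD, and prespecified adjustment lifts power for an assumed 0.7 SD effect from 68% to 79–92%. At 0.2 to 0.3 the like-for-like gain is only about 1 to 3 percentage points. The case for change therefore rests mainly on the baseline value of the outcome and on closing off post hoc choice. It is a worthwhile, inexpensive improvement.

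**What to change.** - Replace the baseline P values with a descriptive table by arm, including standardised differences.
- Before unmasking, name the between-arm model (ANCOVA, or rank ANCOVA if a rank-based method is preferred) and one or two prognostic covariates from visit 1. Put the baseline value of the outcome first. Continued topical cyclosporine or oral tetracycline use (yes/no) is optional.
- Include these covariates whatever imbalance is observed, and state that no covariate is added or dropped because of a baseline P value.
- Keep the unadjusted Wilcoxon comparison as a sensitivity analysis.

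Cost: one or two degrees of freedom, and the between-arm rank sum test becomes an adjusted model, so this changes the analysis method as well as the wording. No new data are needed, since section 7.1 already records current medications and the confocal images at screening/baseline.
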